## 9.0 Ancillary Treatment/Supportive Care

9.1 Blood products and growth factors should be utilized as clinically warranted and following institutional policies and recommendations. The use of growth factors should follow published guidelines of the American Society of Clinical Oncology (42) Update of Recommendations for the Use of Hematopoietic Colony-Stimulating Factors: Evidence-Based, Clinical Practice Guidelines. *J Clin Oncol* 24 (19): 3187 -3205, 2006.

9.2 Patients should receive full supportive care, including transfusions of blood and blood products, antibiotics, and antiemetics when appropriate. **Any blood transfusions administered must be irradiated blood products to reduce risk of transfusion mediated graft versus host disease in CLL and NHL patients receiving T-cell suppressive therapy. Leukocyte reduction of all blood products for patients on protocol is also required.** All blood products and concomitant medications such as antidiarrheals, analgesics, and/or antiemetics received from the first day of study treatment administration until 30 days after the final dose will be recorded in the medical records.

9.3 Concomitant Medications/Vaccinations (allowed & prohibited): Medications or vaccinations specifically prohibited in the exclusion criteria are not allowed during the ongoing trial. If there is a clinical indication for one of these or other medications or vaccinations specifically prohibited during the trial, discontinuation from trial therapy or medication/vaccination may be required. The provider should discuss any questions regarding this with the investigator. The final decision on any supportive therapy or vaccination rests with the investigator and/or the subject's primary physician. However, the decision to continue the subject on trial therapy or vaccination schedule requires the mutual agreement of the Investigator, the provider, and the subject.

9.4 Acceptable Concomitant Medications: All treatments that the provider/investigator considers necessary for a subject's welfare may be administered at the discretion of the provider/investigator in keeping with the community standards of medical care.  
All concomitant medications received within 28 days before the first dose of trial treatment and 30 days after the last dose of trial treatment should be recorded. If changes occur during the trial period, documentation of the changed medication should be recorded.

Note: IVIG replacement therapy for CLL patients is permitted, but recommend to discuss with study chair for continuation.

9.5 Prohibited Concomitant Medications: Subjects are prohibited from receiving the following therapies during the Screening and Treatment Phase of this trial:

- Anti-cancer systemic chemotherapy
- Immunotherapy not specified in this protocol. Note: IVIG replacement is permitted.
- Radiation therapy. Note: Radiation therapy to a symptomatic solitary lesion or to the brain may be allowed after consultation with Investigator.
- Live vaccines within 30 days prior to the first dose of trial treatment and while participating in the trial. Examples of live vaccines include, but are not limited to, the following: measles, mumps, rubella, chicken pox, yellow fever, rabies, BCG, and typhoid (oral) vaccine. Seasonal influenza and pneumonia vaccines for injection are

generally killed virus vaccines and are allowed; however intranasal influenza vaccines (e.g. Flu-Mist®) are live attenuated vaccines, and are not allowed.

- Ongoing chronic steroid therapy with a dose more than equivalent prednisone dose  $\geq 30\text{mg}$  daily for longer than 2 months.

Subjects may receive other medications that the investigator deems to be medically necessary.

9.6 Nausea/vomiting: Nausea and vomiting should be treated aggressively, and consideration should be given in subsequent cycles to the administration of prophylactic antiemetic therapy according to standard institutional practice. Subjects should be strongly encouraged to maintain liberal oral fluid intake.

9.7 Diarrhea: Subjects should be carefully monitored for signs and symptoms of enterocolitis (such as diarrhea, abdominal pain, blood or mucus in stool, with or without fever) and of bowel perforation (such as peritoneal signs and ileus). In symptomatic subjects, infectious etiologies should be ruled out, and if symptoms are persistent and/or severe, endoscopic evaluation should be considered. Steroid therapy should be strongly considered per table 8.3

- All subjects who experience diarrhea should be advised to drink liberal quantities of clear fluids. If sufficient oral fluid intake is not feasible, fluid and electrolytes should be substituted via IV infusion.
- If diarrhea is severe (requiring intravenous rehydration) and/or associated with fever or severe neutropenia (grade 3 or 4), broad-spectrum antibiotics must be prescribed. Patients with severe diarrhea or any diarrhea associated with severe nausea or vomiting **should be hospitalized** for intravenous hydration and correction of electrolyte imbalances.

9.8 Anti-infectives: Subjects with a documented infectious complication should receive oral or IV antibiotics or other anti-infective agents as considered appropriate by the treating investigator for a given infectious condition, according to standard institutional practice. **For CLL patients, it is highly recommended to start PCP and viral prophylaxis while patients are on treatment.**

9.9a Management of Infusion Related Reactions: Acute infusion reactions (which can include cytokine release syndrome, angioedema, or anaphylaxis) are different from allergic/hypersensitive reactions, although some of the manifestations are common to both AEs. Signs and symptoms usually develop during or shortly after drug infusion and generally resolve completely within 24 hours of completion of infusion. Signs/symptoms may include: Allergic reaction/hypersensitivity (including drug fever); Arthralgia (joint pain); Bronchospasm; Cough; Dizziness; Dyspnea (shortness of breath); Fatigue (asthenia, lethargy, malaise); Headache; Hypertension; Hypotension; Myalgia (muscle pain); Nausea; Pruritis/itching; Rash/desquamation; Rigors/chills; Sweating (diaphoresis); Tachycardia; Tumor pain (onset or exacerbation of tumor pain due to treatment); Urticaria (hives, welts, wheals); Vomiting or Diarrhea.

Treatment guidelines for subjects who experience an infusion related reaction associated with administration of MK-3475.

NCI CTCAE Grade	Treatment	Premedication at subsequent dosing
Grade 1 Mild reaction; infusion interruption not indicated; intervention not indicated	Increase monitoring of vital signs as medically indicated until the subject is deemed medically stable in the opinion of the investigator.	None
Grade 2 Requires infusion interruption but responds promptly to symptomatic treatment (e.g., antihistamines, NSAIDS, narcotics, IV fluids); prophylactic medications indicated for $\leq$ 24 hrs	
Stop Infusion and monitor symptoms.
 
Additional appropriate medical therapy may include but is not limited to:
 
IV fluids Antihistamines NSAIDS Acetaminophen Narcotics Corticosteroids
 
Increase monitoring of vital signs as medically indicated until the subject is deemed medically stable in the opinion of the investigator.
 
If symptoms resolve within two hours of stopping drug infusion, the infusion may be restarted at 50% of the original infusion rate (e.g. from 100 mL/hr to 50 mL/hr). Otherwise dosing will be held until symptoms resolve and the subject should be premedicated for the next scheduled dose.
 
Subjects who develop Grade 3 toxicity despite adequate
	
Subject may be premedicated 1.5h (<math>\pm</math> 30 minutes) prior to infusion of MK-3475 with:
 
Diphenhydramine 50 mg po (or equivalent dose of antihistamine).
 
Acetaminophen 500-1000 mg po (or equivalent dose of antipyretic).
 
Additional pre-medication as needed per treating provider's discretion.

NCI CTCAE Grade	Treatment	Premedication at subsequent dosing
	premedication should be permanently discontinued from further trial treatment. If $\geq 3$ cycles of therapy was given, patients will go to observation, otherwise event monitoring.	
Grades 3 or 4 Grade 3: Prolonged (i.e., not rapidly responsive to symptomatic medication and/or brief interruption of infusion); recurrence of symptoms following initial improvement; hospitalization indicated for other clinical sequelae (e.g., renal impairment, pulmonary infiltrates)  Grade 4: Life-threatening; pressor or ventilatory support indicated	
Stop Infusion.
 
Additional appropriate medical therapy may include but is not limited to:
 
IV fluids Antihistamines NSAIDS Acetaminophen Narcotics Oxygen Pressors Corticosteroids Epinephrine
 
Increase monitoring of vital signs as medically indicated until the subject is deemed medically stable in the opinion of the investigator.
 
Hospitalization may be indicated.
 
Subject is permanently discontinued from further trial treatment administration. If <math>\geq 2</math>cycles of therapy was given, patients will go to observation, otherwise event monitoring.
	No subsequent dosing, discontinue the treatment.

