- 11.513 The spleen and/or liver, if considered enlarged before therapy on the basis of a physical examination or CT scan, should not be palpable on physical examination and should be considered normal size by imaging studies, and nodules related to lymphoma should disappear. However, determination of splenic involvement is not always reliable because a spleen considered normal in size may still contain lymphoma, whereas an enlarged spleen may reflect variations in anatomy, blood volume, the use of hematopoietic growth factors, or causes other than lymphoma. Similarly, other organs considered to be enlarged before therapy due to involvement by lymphoma, such as liver and kidneys, must have decreased in size.
- 11.514 If the bone marrow was involved by lymphoma before treatment, the infiltrate must have cleared on repeat bone marrow biopsy. The biopsy sample on which this determination is made must be adequate (with a goal of  $> 20$  mm unilateral core). If the sample is indeterminate by morphology, it should be negative by immunohistochemistry. A sample that is negative by immunohistochemistry but that demonstrates a small population of clonal lymphocytes by flow cytometry will be considered a CR until data become available demonstrating a clear difference in patient outcome.

11.52 **Criteria for Partial Response (PR).** The designation of PR requires all of the following:

11.521 At least a 50% decrease in sum of the product of the diameters (SPD) of up to six of the largest dominant nodes or nodal masses. These nodes or masses should be selected according to all of the following:

- they should be clearly measurable in at least 2 perpendicular dimensions
- if possible they should be from disparate regions of the body
- they should include mediastinal and retroperitoneal areas of disease whenever these sites are involved or  $\geq 50\%$  decrease of other measurements (e.g. skin lymphoma) only measurable by physical exam {Olsen, 2011 #547}
- $\geq 50\%$  decrease of other measurements (e.g. skin lymphoma) only measurable by physical exam

11.522 No increase should be observed in the size of other nodes, liver, or spleen.

11.523 Splenic and hepatic nodules must regress by  $\geq 50\%$  in their SPD or, for single nodules, in the greatest transverse diameter.

11.524 With the exception of splenic and hepatic nodules, involvement of other organs is usually assessable and no measurable disease should be present.

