- An unacceptable adverse event that occurs after the patient received at least 2 cycles of treatment, which in the opinion of the Investigator, precludes further trial participation.

13.5 Event Monitoring: Patients will enter event monitoring for the following reasons:

- If the patient develops evidence of PMD/PD (For CLL Arm A and C: PMD/PD on combination therapy; For B-NHL Arm B: PD on MK-3475 single therapy) during treatment or OBSERVATION by examination, blood counts, or imaging as defined in Sections 11.23, 11.4, 11.54 and 11.61, they will be considered to have progressed and will enter EVENT MONITORING. Refer to Section 4.0 for required tests at PMD/PD.

NOTE: Patients whose only evidence of disease recurrence is by sensitive evaluation of MRD will continue under OBSERVATION in accord with standard clinical practice and will NOT be considered PD.

- Subsequent treatment for CLL or NHL
- Failure to return for an evaluation during OBSERVATION
- Patient refusal of further study treatment or noncompliance
- Patient develops an intercurrent illness that precludes further participation, or requires a prohibited concomitant treatment
- The Investigator withdraws the patient in the patient's best interests
- Administrative reasons (e.g., the patient is transferred to hospice care)
- Pregnancy
- An unacceptable adverse event that occurs during cycles 1-2

**Note:** When a subject discontinues treatment, all applicable activities scheduled for the final trial visit should be performed at the time of discontinuation. Any adverse events which are present at the time of discontinuation/withdrawal should be followed in accordance with the safety requirements outlined in Section 10.0 -Assessing and Recording Adverse Events

13.6 A patient is deemed ineligible if after registration, it is determined that at the time of registration, the patient did not satisfy each and every eligibility criteria for study entry. The patient will go directly to the event-monitoring phase of the study:

- If the patient received treatment, all data up until the point of confirmation of ineligibility must be submitted. Event monitoring will be required per Section 18.0 of the protocol.
- If the patient never received treatment, on-study material and the End of Active Treatment/Cancel Notification Form must be submitted. No further data submission is necessary.

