- 13.7 A patient is deemed a major violation, if protocol requirements regarding treatment in cycle 1 of the initial therapy are severely violated that evaluability for primary end point is questionable. All data up until the point of confirmation of a major violation must be submitted. The patient will go directly to the event-monitoring phase of the study.
- 13.8 A patient is deemed a cancel if he/she is removed from the study for any reason before any study treatment is given. On-study material and the End of Active Treatment/Cancel Notification Form must be submitted. No further data submission is necessary.

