## 16.0 Statistical Considerations and Methodology

16.1 Overview: This Phase II study will utilize a one-stage binomial design in each arm independently (Arms A, B, and C) to assess the overall response rate associated with single-agent MK-3475 in patients with relapsed and progressive CLL/SLL, including CLL patients with Richter's transformation (RS) or Hodgkin's transformation (Arm A and Arm C) and other types of relapsed and progressive low grade B cell NHL including FL, WM and marginal zone lymphoma (Arm B).

16.11 Endpoint: The primary endpoint of this trial is the proportion of patients who achieve a confirmed response to single-agent MK-3475. A confirmed response is defined to be a PR, nPR, CCR, CRi or CR (Arms A and B) or CMR, PMR, PR, or CR (Arm C) noted as the objective status at any time while on single-agent MK-3475. All patients meeting the eligibility criteria who have signed a consent form and have begun treatment will be evaluable for response, with the exception of patients determined to be a major violation.

16.12 Sample Size: This study is expected to require a maximum of 23 evaluable patients each in Arm A and Arm B. We anticipate accruing 1 additional patient in each arm to account for ineligibility, cancellation, major treatment violation, or other reasons. Therefore, this study is expected to accrue between 46 - 48 patients in these two arms.  
As of MCCC Addendum 3, due to promising response observed in CLL patients with Richter's transformation, an additional arm (Arm C) with 17 evaluable patients is added to the trial. We anticipate accruing 3 additional patients to account for ineligibility, cancellation, major treatment violation, or other reasons for a total of 20 patients on Arm C. These patients will be accrued to allow better evaluation of response and toxicity of single agent MK 3475 in patients with Richter's transformation. This study is now expected to accrue a maximum of 68 patients.

16.13 Accrual Rate and Study Duration: The anticipated accrual rate is approximately 2-4 patients per month. Therefore, the accrual period for this phase II study is expected to be approximately 2-3.0 years. The final analysis can begin as soon as the last patient has been observed for 6 months, or at approximately 3.0-3.5 years.  

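### Radiotherapy permitted during treatment can be credited to MK-3475 as a response, because no rule sets aside an irradiated lesion

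*Combined protocol and SAP*

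**What the plan says.** Section 9.5 opens with "Subjects are prohibited from receiving the following therapies during the Screening and Treatment Phase of this trial" and lists radiation therapy. A note to that item reads "Radiation therapy to a symptomatic solitary lesion or to the brain may be allowed after consultation with Investigator". The exception therefore operates while MK-3475 is being given.

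Sections 16.11 and 16.311 define success as a qualifying response "noted as the objective status at any time while on single-agent MK-3475". Patients who are eligible, have consented and "have begun treatment will be evaluable for response, with the exception of patients determined to be a major violation". Section 13.7 confines that exception to the start of therapy: "A patient is deemed a major violation, if protocol requirements regarding treatment in cycle 1 of the initial therapy are severely violated".

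The response criteria are silent on irradiated lesions. For Arm B, 11.521 asks for "At least a 50% decrease in sum of the product of the diameters (SPD) of up to six of the largest dominant nodes". The CT column of the Lugano table (11.61), used for Richter's patients, applies the same 50% threshold to up to six targets, and its PET column scores uptake. Sections 11.2 and 11.4 (CLL) and 11.7 (Waldenstrom) do not mention radiation either.

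Section 13.5 moves a patient to event monitoring if he or she "requires a prohibited concomitant treatment", and separately on later therapy for CLL or NHL. It places the radiotherapy allowed by 9.5 in neither group.

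**The concern.** The primary goal (2.11) is the response rate to MK-3475 alone. If a permitted local treatment shrinks the lesion on which response is measured, the recorded PR, CR, PMR or CMR is not evidence about the drug. The bias runs one way, toward declaring activity.

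It matters because each arm is decided on five successes (16.211, 16.231). One converted patient turns 4/23 (17.4%, ineffective) into 5/23 (21.7%, may proceed), or 4/17 (23.5%) into 5/17 (29.4%). Sections 3.15 and 3.16 ask only for measurable disease of at least 1.5 cm, and 3.15 says that one lesion is enough, so the irradiated lesion can be the only target. The protocol deals with other sources of misclassification: tumor flare is kept out of progression, and starting combination therapy for stable disease censors PFS. It has no parallel rule for radiotherapy.

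**Working it through.** **Inputs.** Arms A and B: n = 23, null 10%, target 30%, pass at 5 or more (16.21, 16.211). Arm C: n = 17, null 15%, target 40%, pass at 5 or more (16.23, 16.231). The documents give no frequency of on-treatment radiotherapy, so the conversion shares below are assumptions.

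**Step 1. Reproduce the plan.** The exact tail P(Bin(n, p) ≥ 5) gives 0.073 at 10% and 0.864 at 30% for n = 23. It gives 0.099 at 15% and 0.874 at 40% for n = 17. These round to the stated 0.07, 0.86, 0.10 and 0.87. The design figures are correct.

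**Step 2. When can one irradiated lesion make a response?** Suppose it holds share s of the baseline sum of products, disappears, and the rest is unchanged. The sum then falls by s, so the 50% threshold is met when s ≥ 0.5. A sole target has s = 1. On PET, a complete metabolic response is possible if the irradiated lesion was the only site still avid. Exposure by group:
- Nodal Arm B and Richter's patients (Arm C and transformed Arm A): exposed as above. Arm B PR also requires no growth of other nodes, liver or spleen and no new site.
- CLL without transformation: PR needs two of lymphocytes, nodes and liver/spleen (where abnormal at baseline) plus a blood-count feature, held for at least 2 months (11.22). Exposure is small, except in SLL measurable only by CT (11.227).
- Waldenstrom followed by IgM: PR needs a fall of at least 50% in monoclonal IgM (11.7). Exposure is small.

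**Step 3. A share q of would-be non-responders is converted.** The apparent null rate is p' = p0 + (1 − p0)q, and the false-positive rate is P(Bin(n, p') ≥ 5).

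| q (assumed) | A/B: p' | A/B: false-positive rate | C: p' | C: false-positive rate |
|---|---|---|---|---|
| 0 | 0.100 | 7.3% | 0.150 | 9.9% |
| 0.5% | 0.1045 | 8.5% | 0.1543 | 10.8% |
| 1% | 0.109 | 9.8% | 0.1585 | 11.9% |
| 2% | 0.118 | 12.7% | 0.167 | 14.1% |
| 5% | 0.145 | 23.3% | 0.1925 | 21.7% |

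At the null, the expected number converted is n(1 − p0)q. For q = 0.5% this is 23 × 0.90 × 0.005 = 0.10 patients in Arm A or B and 17 × 0.85 × 0.005 = 0.07 in Arm C. For q = 5% it is 1.04 and 0.72.

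**Step 4. Conditional on one certain conversion.** P(Bin(22, 0.10) ≥ 4) = 17.2% and P(Bin(16, 0.15) ≥ 4) = 21.0%.

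**Step 5. Cost of the rule.** In the least favorable case, an affected patient counts as a non-responder and stays in the denominator. With one such patient, power is P(Bin(22, 0.30) ≥ 5) = 83.6% (from 86.4%) in Arms A and B and P(Bin(16, 0.40) ≥ 5) = 83.3% (from 87.4%) in Arm C. The false-positive rates fall to 6.2% and 7.9%.

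**The case against.** The best counter-argument is Section 13.5. Radiation aimed at a lymphoma lesion can be read as later therapy for CLL or NHL. On that reading the patient goes to event monitoring, is no longer on single-agent MK-3475, and later shrinkage falls outside the endpoint window. This stands as a possible reading, and it rules out saying flatly that radiation shrinkage counts. It does not close the gap: 13.5 does not classify this radiotherapy, and the reading would leave the 9.5 exception little purpose during treatment.

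Confirmed progression also narrows the exposed group. It takes Arm B patients off treatment (13.2). In Arms A and C, progression, or stable disease at month 3, allows a signal inhibitor to be added, which ends the single-agent window (7.3, 13.1). That leaves patients irradiated without confirmed progression and still on MK-3475 alone.

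Three stronger readings should be resisted. A reader might infer that all arms are equally exposed; the CLL and Waldenstrom criteria in Step 2 say otherwise. A reader might take 17.2% and 21.0% as the expected error rates; they assume that a conversion has certainly happened. A reader might treat an irradiated lesion as a likely treatment failure; the exception requires only that the lesion be symptomatic, and the protocol separates tumor flare from progression.

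**Conclusion.** The gap is real. Read together, 9.5, Section 11 and 16.311 allow radiation shrinkage to be counted as a single-agent response, and no evaluability rule prevents it. The documents support can count, not does count, and they do not show that any such response has occurred.

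The size depends on a frequency that is not given. At conversion shares of 2% or less the false-positive rate stays at or below 12.7% (Arms A and B) and 14.1% (Arm C); at 5% it more than doubles in each. The Arm A figures are an upper bound, because they apply the same share to CLL patients without transformation. The event is probably uncommon, but one case can decide an arm and a simple rule prevents it, so it should be fixed before the final analysis.

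The silence extends to secondary endpoints. PFS and duration of response have no rule for radiotherapy, and for treatment-free survival and time to next treatment it is undefined whether it counts as subsequent treatment.

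**What to change.** State in Section 11 and 16.311 that a lesion irradiated on study is not used to establish response from that date. If no un-irradiated measurable disease remains, best response is the one recorded before radiation, and the patient stays in the denominator. List these patients with the date and site of radiation.

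Reconcile 9.5 with 13.5, so that it is clear whether the permitted radiotherapy ends protocol treatment. Separately, and for analysis only, state how it is handled in PFS, duration of response, treatment-free survival and time to next treatment (16.321 to 16.323, 16.325). Keep these two steps apart: simply labeling it subsequent treatment would also trigger the 13.5 exit and contradict 9.5. Whether radiotherapy may be given is a clinical matter, and this change leaves it alone.

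In Arm C the work is one rule and one case-report flag. Arms A and B are closed to accrual, so there the rule is applied from existing treatment records, which means a retrospective review. The statistical price is that a few genuine responses may be lost, with power lower by about 3 points (Arms A and B) or 4 points (Arm C) if one patient is affected.
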